## Figure 2: Intervention design

### Protocol/IRB Change Log\* (not all IRB changes necessitated protocol changes):

#### 2/2019

1. Modified consent form to include Certificate of Confidentiality language

#### 9/2019

1. Added new personnel ([name], research assistant)
2. Updated flyer and consent forms to include more details, including increasing reimbursement offered (increased total reimbursement from \$50 to \$100)

#### 12/2019

- Updated screening script to match consent form and flyer language
- We inserted the short form, used in place of the long form (where appropriate), for quantitative measures to decrease participant burden. Measures that will use the short form include:
  - Zarit Burden Interview-SF 12 (ZBI-12)
  - Intolerance of Uncertainty (IUS-12)
  - Cognitive Emotion Regulation-Short Form (CERQ-18)
  - PROMIS General Self-efficacy-Short Form 4a
  - PROMIS Self-efficacy Manage Emotions-Short Form 4a
  - PROMIS Anxiety-Short Form 4a
  - PROMIS Anger-Short Form 5a
  - PROMIS Emotional Support-Short Form 4a
  - PROMIS Instrumental Support-Short Form 4a
  - PROMIS Informational Support-Short Form 4a
- Pre-participation Interview: guided questions added for participants to share their thoughts about mindfulness, telephone sessions, and comfortability with technology
- Mindfulness scale: substituted Cognitive and Affective Mindfulness Scale-Revised (CAMS-R) for Self-Compassion Scale (SCS). Questions for CAMS-R are shorter. The research team thought this would decrease the questionnaire burden for participants.
- Added new personnel ([name], co-investigator)

#### 3/2020:

1. In response to COVID, we changed the protocol as follows:
  - a. All assessments and consent processes could be completed over the telephone (in home left as an option)

b. The 3.5 hour in-person retreat was changed to a 1.5 hour video-conference retreat

**4/2020:**

1. Added new recruitment methods in response to COVID, including email announcements, radio/newspaper ads, and Facebook ads
2. Added new personnel ([name], [name], research assistants)
3. Modified eligibility criteria for care recipients. Recipients would be considered eligible if care recipient has received a diagnosis of dementia, OR receives a score of 2 or higher rating by the primary caregiver on the AD-8 scale OR at least an 8 on the FAST scale.

**6/2020:**

1. Minor flyer update to emphasize over the phone options
2. Expanded geographic eligibility area to include all of rural Eastern NC (and defined these)
3. Received IRB approval to allow community partners to share potential subjects contact information with the team, if permission by the potential subject is given

**7/2020:**

1. Added website site (Study Pages) and NC registry for Brain Health/Duke Family Caregiver e-news as recruitment sources

**8/2020:**

1. Updated study personnel, added [name] as study physician

**9/2020:**

1. Consent modified to state online retreat length could vary (up to 4 hours)

**10/2020:**

1. Added questions to enrollment process to assess home internet status, for purposes of distribution of tablets

**12/2020**

1. Added emergency contact information and a UNC consent addendum to allow unencrypted texting/emailing for primarily to allow scheduling and reminders of study-related activities
2. Added protocol for emergency situations over the phone

**7/2021**

1. Added [name] to the research team

**10/2021**

1. Added script/instructions to assessments to emphasize voluntary nature/ability to skip questions

## PRÉCIS

### **Study Title: Easing the Burden of Dementia Caregiving: A Telephone-delivered Mindfulness Intervention for Rural, African American Families**

#### **Objectives**

SPECIFIC AIM 1: To determine the feasibility and acceptability of a telephone-delivered mindfulness training intervention (TMT) in decreasing caregiver burden among rural, African American, informal caregiving teams of people with dementia.

SPECIFIC AIM 2: To explore, on a preliminary basis, the effects of the training on caregiver burden and relevant secondary outcomes for both caregiving team members, including (1) emotion regulation; (2) tolerance of uncertainty; (3) emotional and physical health; (4) family conflict within the informal caregiving team; and (5) self-efficacy.

SPECIFIC AIM 3: To explore comfort with and willingness to adopt technologies (e.g. telephone-based, web-based) to access mindfulness practices and existing caregiving educational resources.

#### **Design and Outcomes**

The proposed study utilizes a single-group, uncontrolled design to assess the feasibility and acceptability of telephone-delivered mindfulness training designed to alleviate caregiver burden for rural caregivers of African American individuals with moderate to severe dementia. A care partner—the person who provides the most support in addition to the primary caregiver—is included in the intervention. The primary outcome is feasibility as assessed by an 85% retention rate with completion of at least 6 of the intervention sessions. Pre- and post-participation interviews will assess acceptability.

At baseline, after obtaining informed consent, study staff will interview primary caregivers in their homes (or via a phone call post-COVID) and will administer a set of questionnaires, including the 12-item Zarit Burden Interview as well as measures of:

- 1) family satisfaction;
- 2) tolerance of uncertainty;
- 3) cognitive emotion regulation;
- 4) general self-efficacy;
- 5) anxiety and anger;
- 6) self-efficacy in managing emotions;
- 7) global physical health;
- 8) family conflict;
- 9) social support (emotional, instrumental, informational);

*10) meaning and purpose;*

*11) cognitive and affective mindfulness*

Study staff will interview the care partner in person or over the telephone. After the 8-week intervention, study staff will interview the caregiver (in the home, or via telephone), care partners (on the telephone) once more, and administer the questionnaires.

### **Interventions and Duration**

The intervention consists of mindfulness training delivered by telephone once weekly for 8 weeks. The intervention also includes one weekend part-day retreat. The intervention, based on Kabat-Zinn's mindfulness-based stress reduction (MBSR) and adapted for this study population, emphasizes the following: 1) mindful experiencing, including mindfulness of body sensations, feelings, thoughts and emotions ; 2) mindful communication, including non-verbal mindfulness, mindful listening, and mindful speaking; and 3) mindful compassion for self and others.

### **Sample Size and Population**

Planned study participants include 32 adult caregivers, aged 18 and older, who live with or near an African American dementia care recipient and provide at least four hours of care per day. Additional participants include an additional adult, the care partner, who the caregiver identifies as another person who helps with the care. This person may be a blood relative or a non-blood relative. Hence, 32 caregiver-care partner dyads comprise the study population.

## **PARTICIPATING STUDY SITES**

Not applicable.

## **1 STUDY OBJECTIVES**

### **1.1 Primary Objective**

SPECIFIC AIM 1: To determine the feasibility and acceptability of a telephone-delivered mindfulness training intervention (TMT) in decreasing caregiver burden among rural, informal caregiving teams caring for African Americans with dementia.

Hypothesis 1: TMT will be feasible within the informal caregiving teams. Feasibility is established when 85% (95% CI: 72.5, 97.5) of participants in the telephone-delivered mindfulness training intervention complete at least six sessions of the intervention.

Hypothesis 2: The adapted TMT will be acceptable to informal caregiving teams as evidenced by an 85% (95% CI: 72.5, 97.5) endorsement of the program in post-participation interviews.

### **1.2 Secondary Objectives**

SPECIFIC AIM 2: To explore, on a preliminary basis, the effects of the training on caregiver burden and relevant secondary outcomes for both caregiving team members, including:

Hypothesis 1: Compared with baseline levels, we hypothesize that mindfulness training will reduce caregiver burden (Zarit Burden Interview).

Hypothesis 2: Compared with baseline levels, we hypothesize that mindfulness training will improve emotion regulation by increasing positive coping styles (acceptance, positive refocusing, positive reappraisal) and decreasing negative coping styles (rumination, catastrophizing, self-blame) as measured by the Cognitive Emotion Regulation Questionnaire.

Hypothesis 3: Compared with baseline levels, we hypothesize that mindfulness training will increase tolerance of uncertainty as measured by (an adapted form of) the Intolerance of Uncertainty Scale.

Hypothesis 4: Compared with baseline levels, we hypothesize that training in mindful communication will increase perceived social support among the caregivers (PROMIS Social Support short forms).

Hypothesis 5: Compared with baseline levels, we hypothesize that training in mindful communication reduce family conflict around caregiving (Family Conflict Scale).

Hypothesis 6: Compared with baseline levels, we hypothesize that mindfulness training will reduce anger and anxiety (PROMIS scales).

Hypothesis 7: Compared with baseline levels, we hypothesize that mindfulness training increase global self-perceived physical health (PROMIS short forms).

Hypothesis 8: Compared with baseline levels, we hypothesize that mindfulness training increase meaning and purpose (PROMIS short form).

Hypothesis 9: Compared with baseline levels, we hypothesize that mindfulness training along with a caregiver resources handbook will increase caregiver general and emotional self-efficacy (PROMIS scales).

Hypothesis 10: Compared with baseline levels, we hypothesize that mindfulness training will increase family satisfaction (Family Satisfaction Scale).

Hypothesis 11: Compared with baseline levels, we hypothesize that mindfulness training will increase mindfulness (Cognitive and Affective Mindfulness Scale).

**SPECIFIC AIM 3:** To explore comfort with and willingness to adopt technologies (e.g. telephone-based, web-based) to access mindfulness practices and existing caregiving educational resources.

As part of intervention planning, using interviews, we will investigate comfort with a smartphone/tablet. We will implement the tablets among half of the intervention groups so that we can compare acceptance between groups with and without the technology.

## **2 BACKGROUND AND RATIONALE**

[figure not shown]
### **2.1 Background on Condition, Disease, or Other Primary Study Focus**

The number of individuals and families impacted by Alzheimer's disease and related dementia (ADRD) is projected to triple by 2050 and many of those impacted will be African Americans (AAs). Further, many older AAs live in rural areas and experience disadvantages by living in areas with fewer resources and poorer infrastructure. Given that AAs and rural older adults are often disproportionately affected by ADRD, this research seeks to meet the need for culturally and geographically tailored research for rural AA caregivers of older adults with ADRD. Most families, including AA families, provide dementia care in the home and when compared with other caregivers (CGs), dementia CGs experience higher levels of physical, financial, and emotional burden, including anxiety and stress as well as higher rates of family discord. One study reported over 50% of spousal CGs and over 80% of adult children CGs endorsed some level of family conflict. Some researchers have called dementia 'the great divider', as caregiving stress tends to accentuate long-standing interpersonal issues between family members. Aspects of family functioning most strongly associated with caregiving burden include ineffective communication and difficulties around roles (i.e. distribution of caregiving tasks). In AA families, often a cultural expectation of high family involvement exists, so family conflict around roles and provision of social support may be particularly distressing. Despite these findings, few CG interventions address family relationship difficulties.

We know that race and cultural experiences, ways of coping, and ways of seeking help often differ for AA compare with caregivers of other ethnicities. Evidence also suggests that, contrary to previous findings, AA caregivers, who are likely to be adult children, also experience high levels of anxiety and distress. Therefore, within-group studies of African Americans, and other racial minorities, are needed to provide characteristics and processes critical for tailored interventions. Hence, **innovative theory-based programs**, culturally and geographically tailored to rural AA populations, are needed to ease the burden of dementia-related caregiving in rural AA populations.

## 2.2 Study Rationale

**Pearlin et al.'s Stress Process Model** posits complex relationships between background characteristics (demographics), primary stressors (care recipient neuropsychiatric symptoms and level of functional and cognitive impairment), secondary stressors/outcomes (interpersonal and intrapersonal strain) and caregiver health outcomes (physical and mental health) all mediated by coping and social support. The theory conceptualizes family conflict as a secondary, but potent source of stress outside of the caregiving situation, with both direct and indirect effects on negative caregiver (CG) outcomes. Family conflict is associated with high CG burden and negative CG mental and physical health outcomes, even after controlling for CG and care recipient characteristics typically associated with stress outcomes. Moreover, there is evidence that the structured, often repetitious ways that family members interact with one another, can either promote positive CG outcomes or contribute to CG distress in families caring for someone with dementia. In addition to these interpersonal strains, intrapersonal stressors such as role captivity and poor self-efficacy both result from and contribute to negative health outcomes.

**Figure 1: Stress process and uncertainty theories informing caregiver mindfulness training**

**Mishel's Reconceptualized Uncertainty in Illness Theory (RUIT),** like her original theory, conceptualizes uncertainty as either a danger or an opportunity. Unlike the original theory, the reconceptualized model recognizes that when the outcome is negative, such as decline of a relative, appraisal of uncertainty as negative versus positive can change over time. In a study applying the RUIT to dementia caregiving, uncertainty was seen to impact the appraisal of primary stressors, making it conceptually consistent with other mediators. Mindfulness has been associated with cognitive flexibility, a related construct. Accordingly, in our proposed intervention, we hypothesize that mindfulness training could enhance the CG's shift from a resistance to uncertainty to an acceptance of it as a natural part of life. Similarly, mindfulness

training can shift emotion regulation strategies from negative (e.g., self-blame) to positive (e.g., planning). Additionally, the proposed focus on improving family conflict should affect perceived social support, another mediator of health outcomes, thereby leading to greater self-efficacy and positive emotions.

### **Mindfulness-based Stress Reduction for reducing burden in dementia caregivers.**

Mindfulness meditation has been described as “a behavioral technique involving the intentional self-regulation of attention to present-moment experience, combined with release of cognitive fixation on thoughts (whether simple images or complex storylines) regarding the past or future.” Through training in mindfulness, individuals learn to evoke and sustain a non-judgmental state of present-moment awareness. Research has shown that mindfulness training programs such as Mindfulness-based Stress Reduction (MBSR), which also incorporate exercises to generate compassion for oneself and others, result in reduced stress, improved coping, and a host of improved physical and psychological health outcomes. Mindfulness training programs have been adapted and successfully utilized for a wide range of conditions, populations, and cultures including in AAs and in CGs. Studies with AAs have shown mindfulness training to be culturally acceptable and feasible. Studies with CGs, including informal CGs of persons with dementia, have shown that mindfulness interventions can decrease CG burden and improve coping skills, including decreased emotion-based coping and increased tolerance for uncertainty, as well as improve psychological well-being and quality of life. Two studies have also shown mindfulness to improve relationship quality and communication.

In order to increase geographic accessibility, mindfulness training programs have been successfully adapted to distance-based formats, particularly involving use of the internet and occasionally have incorporated smart-phone or telephone-delivered mindfulness training formats. An additional advantage of distance-based formats for CGs is their flexibility in terms of the CG’s often restricted and demanding lifestyle. For rural caregivers, a telephone-delivered mindfulness program would seem to be particularly accessible, useable, and feasible, overcoming both distance and infrastructure barriers. Moreover, such a program would easily lend itself to facilitating communication between CG family members, including those who are geographically distant, thereby increasing our intervention’s reach.

**Developing a Telephone-Delivered Mindfulness Training Intervention (TMT) for Care Teams.** In light of the above findings, and relying on [name] extensive experience in adapting mindfulness-training programs and [name] extensive experience working with African American caregivers, we plan to implement a telephone-delivered mindfulness training intervention that will incorporate:

- 1) Training for primary caregivers (CG) and their caregiving partner (CP) in an 8-week, telephone-based, mindfulness-based stress reduction (MBSR) program, which places additional emphasis on training in the following:
  - a. mindful experiencing, including mindfulness of feelings and body sensations as

- well as thoughts and emotions;
- b. mindful communication, including non-verbal mindfulness, mindful listening, and mindful speaking; and
- c. mindful compassion for self and others.

2) Groups of up to eight participants (four CG-CP pairs) plus an instructor, on a shared telephone line; and

Additionally, homework assignments for CG will involve listening to exercise recordings via a dial-in telephone line or computer tablet and assignments for CG-CP dyads (e.g. mindful listening and communication practices) as well as CG mindfulness practices in the presence of CRs (e.g. mindful eating, and mindful listening). Based on theory and evidence from previous mindfulness studies, we believe that this intervention holds promise of making a significant impact on reducing burden in AA rural CGs.

[figure not shown]
The study pilots a telephone-delivered mindfulness-training intervention (TMT) for caregiving teams (rather than in-person or web-based) aimed at reducing caregiver burden. Our rationale is that members of rural communities are less likely to have access to the internet, but have high likelihood of some form of telephone service, and are limited by caregiving responsibilities in their ability to attend training programs. Currently, the intervention is planned for eight weekly, one-hour telephone sessions along with one 1.5-hour retreat. Adjustments to the format are possible, based on input from key informants and the Advisory Council.

In pre-post studies, mindfulness training in pre-post studies has shown a moderate positive effect on clinical outcomes such as depression, anxiety, and physical conditions with a Hedge's  $g$  of 0.57 (95% CI 0.5, 0.64). A meta-analysis of studies of mindfulness training for caregivers showed consistently positive effects on psychological outcomes.

Adverse events are rarely reported in mindfulness training studies. However, the training prompts participants to attend to emotions, thoughts, and physical sensations, some of which may be unpleasant. Hence, emotional discomfort or distress (EDD) may arise for some participants. Usually, EDD resolves quickly with guidance from an experienced instructor and, as participants become more skilled in mindfulness, they recover from EDD more quickly. Mindfulness training has the potential to exacerbate dissociation in susceptible individuals—therefore, it is important to exclude such individuals unless the program is monitored by an experienced mental health clinician.

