## **4 SELECTION AND ENROLLMENT OF PARTICIPANTS**

### **4.1 Inclusion and Exclusion Criteria**

Informal caregiving teams will be composed of a primary and secondary informal caregiver, as defined as:

*any relative, partner, friend or neighbor who has a significant personal relationship with, and provides a broad range of assistance for, an older person or an adult with a chronic or disabling condition [in this case, Alzheimer's Disease or a related dementia]. These individuals may be primary or secondary caregivers and live with, or separately from, the person receiving care. (Family Caregiver Alliance, [www.caregiver.org](http://www.caregiver.org))*

The primary caregiver (CG) are adults who must:

- Care for a family member with dementia who identifies as Black or African American
  - Defined: Care recipient must have a diagnosis of dementia (reported by caregiver) or have a score of at 2 or higher on the AD-8 or a score of 8 or higher on the Functional Activities Questionnaire (FAQ).
- Provide regular, daily care (at least 4 hours per day) for a family member who has dementia
- Have another adult care partner (CP) who is willing to participate; someone who shares caregiving or helps make decisions regarding the person with dementia or Alzheimer's disease (may be remote and family member or friend)
- Have a telephone and be willing to participate in weekly calls
- Live in rural areas in Eastern North Carolina.
  - Defined: Eastern is defined as east of Wake County NC; rural is defined as listed as rural within the website <https://www.ruralhealthinfo.org/am-i-rural>

The primary caregiver is excluded if they:

- Are receiving active treatment for cancer
- Have been hospitalized 3 or more times in the last year

The care partner is eligible if they are 18 or older, have a telephone and are willing to attend weekly sessions. Care partners do not need to be living in the same geographic region as the primary caregiver.

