#### Consenting Procedure

Prior to enrollment, interested caregivers will have an opportunity to hear more details about the study. If they continue to be interested, they will provide a telephone consent for review of eligibility and collection of demographic information. If they are eligible and wish to participate in the intervention, study staff (research assistant and/or project manager) will make an appointment for a home visit for enrollment and baseline assessments of the caregiver and/or care partner (during/post-COVID, this changed to a phone appointment). At that time, study procedures will be reviewed again and the caregiver will provide written informed consent (verbal consent and consent addendum for unencrypted messaging post-COVID).

The caregiver will identify a care partner and, with their permission, provide contact information to the study staff. Because care partners may live in a distant geographic location, their consent may be obtained by verbal consent over the telephone.

Screening and consenting can take place at the same time or in two different calls, at the discretion of the care partner.

If changes are made in the study that affect the risk of the intervention before completion of their part of the study, study staff will contact participants again to review a revised consent. Participants who have completed the study will receive a letter explaining the increased risks.

Physical, signed consent documents are stored in a consent binder, to be locked in a portable file cabinet. Study staff will upload the consent documents into the study REDCap site. At intervals, study staff will transport the consent forms and all paper assessments to the project manager to be locked in a file cabinet controlled by the PIs. Once verbal consent processes are in place, verbal consent will be documented on consent forms by the research staff obtaining consent, and stored using TEAMS.

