#### Screening

Caregivers must be screened within 5 weeks of the baseline assessment. It is anticipated that class sessions will begin within four weeks of baseline assessments for each caregiver and care partner.

- At the time of the screening call, the caregiver will verify that they provide at least 4 hours of care per day to the care recipient.
- The caregiver will also verify that they have a family member or friend who assists with care and who is likely to be agreeable to participation in the telephone mindfulness sessions.

- At the time of the baseline visit, the eligibility criteria will be reviewed and completed via an inclusion/exclusion checklist.
- The caregiver will obtain permission for contact from the care partner and give this information to the study staff.

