#### 6.1.2. Enrollment, Baseline, and/or Randomization

##### Enrollment

The first enrollment date is defined as the date that the primary caregiver reviews and signs the written informed consent document. A primary caregiver may still choose to withdraw from the intervention prior to the first intervention session. The primary caregiver will become ineligible for the first intervention session if a care partner does not agree to participate. Hence, a second definition of enrollment, akin to the point of randomization, is the date of the first intervention session. Each individual who participates in the first class session will be considered to be a participant in the intervention. The date of enrollment (baseline assessment) and attendance at the first class session are recorded in the secure study database, REDCap.

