#### 6.1.3. Follow-up Visits

- **Visits 2-6 (Week 2 – Week 5):**  
(Telephone class sessions may be delayed by one week for unavoidable circumstances, e.g., instructor illness, inclement weather)
  - The instructor will submit information on intervention attendance weekly
  - Study staff will call participants to inquire about practice and adverse events at least once during this period
- **Visit 7 (Week 5.5)**  
Retreat may be delayed by one week for unavoidable circumstances, e.g., instructor illness, inclement weather
  - The instructor will submit information on intervention attendance
- **Visits 8-10 (Week 6 – Week 8)**  
Telephone class sessions may be delayed by one week for unavoidable circumstances, e.g., instructor illness, inclement weather
  - The instructor will submit information on intervention attendance weekly
  - Study staff will call participants to inquire about practice and adverse events at least once during this period

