## 7 **SAFETY ASSESSMENTS**

The risks leading to adverse experiences for participants enrolled in the study are minimal, but do exist. Potential adverse experiences for participants as a result of the telephone-delivered mindfulness intervention include:

- Emotional or psychological discomfort or distress, including:
  - Avoidance
  - Agitation
  - Anxiety
  - Difficulty focusing
  - Irritability
  - Nervousness
  - Obsessive thoughts
  - Panic
  - Restlessness
- Physical symptoms associated with emotional/psychological discomfort or distress:
  - Body or joint aches (resulting from intervention practices)
  - Headaches (resulting from intervention practices)
  - Heavy sweating (without performing strenuous activity)
  - Hyperventilation or rapid breathing (without performing strenuous activity)
  - Nausea or gastrointestinal problems (outside of sickness)
  - Rapid heart rate (without performing strenuous activity)

Study staff will encourage participants that they do not have to answer any questions that make

them feel uncomfortable on study questionnaires. During intervention sessions, participants will be encouraged to participate, but can choose not to do an activity that makes them feel uncomfortable. Study staff and the intervention instructor will make participants aware of the experiences that can occur prior and during their time in the study. Study staff will encourage participants to report emotional distress/discomfort and physical symptoms during intervention sessions and through follow-up calls with study staff, which will occur up to 3 times during the intervention. Adverse events will be captured using the Periodic Telephone Administered Adverse Event Monitoring Form.

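### Section 2.2 calls for excluding people susceptible to dissociation unless a mental health clinician monitors the program, but the visible eligibility and screening text has no such exclusion, and Section 7 describes nobody in that clinician role

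*Combined protocol and SAP*

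**What the plan says.** Section 2.2 (Study Rationale) discusses two kinds of harm. Ordinary emotional discomfort is expected to pass quickly for most people with help from an experienced instructor. Dissociation is treated separately and more strictly. The protocol says the training may make it worse in susceptible people, and so "it is important to exclude such individuals unless the program is monitored by an experienced mental health clinician".

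Section 4.1 sets eligibility. Caregivers must be adults and meet five inclusion criteria. They have two exclusions: current cancer treatment, and "Have been hospitalized 3 or more times in the last year". For the second dyad member, "The care partner is eligible if they are 18 or older, have a telephone and are willing to attend weekly sessions". No care partner exclusions are listed.

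Section 6.1.1 describes the screening call, which confirms hours of care and a likely care partner. Then: "At the time of the baseline visit, the eligibility criteria will be reviewed and completed via an inclusion/exclusion checklist". For care partners, "Screening and consenting can take place at the same time or in two different calls, at the discretion of the care partner".

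Section 7 relies on telephone check-ins by study staff and prompts from the instructor. Events are reviewed by the principal investigators and the Study Physician (medical officer), and the Safety Monitoring Committee has oversight.

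**The concern.** The protocol sets its own either/or safety condition, so no outside standard is needed to judge it. A reader expects to find either an entry criterion in 4.1 or a named clinical monitoring role in Section 7. The first is absent, and the second is not described.

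Staff who follow 4.1 and 6.1.1 as written could enrol a susceptible caregiver or care partner without asking the question. Whether the alternative safeguard would then protect that person cannot be told from the text. Participant safety is at stake, along with agreement between the rationale and the operative sections. Alpha, power and the analysis methods are not affected.

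**Working it through.** The plan states no figure for this point, so the check sets the sections side by side.

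**Exclusion branch: eligibility (4.1)**

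| Group | Conditions listed | Number | On dissociation or mental health |
|---|---|---|---|
| Caregiver | Adult | 1 | 0 |
| Caregiver | Inclusion: care recipient with dementia, daily care, care partner, telephone, rural residence | 5 | 0 |
| Caregiver | Exclusion: cancer treatment, hospitalizations | 2 | 0 |
| Care partner | Age, telephone, willingness | 3 | 0 |
| Total | 1 + 5 + 2 + 3 | 11 | 0 |

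The hospitalization exclusion covers any cause and applies to caregivers only.

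**Exclusion branch: screening (6.1.1).** The call verifies hours of care and a care partner. The baseline checklist is described as reviewing the eligibility criteria, with no further item mentioned. Nothing in the visible steps asks about dissociation or psychiatric history.

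**Monitoring branch.** The roles that could fill it are:
- principal investigators and Study Physician, who judge severity and relatedness (7.1, 7.5, 7.6);
- the Safety Monitoring Committee, which receives all events twice a year and serious ones within 24 hours (7.4), and meets at least four times (7.6);
- the person who listens to every session (10.2), whose stated tasks are rating adherence to the protocol and discussing deviations with the instructor;
- the instructors, who are described as experienced in mindfulness (5.2).

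None is described as a mental health clinician. The roster is not available and names are masked, so credentials cannot be checked.

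**Other safeguards**

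| Safeguard | Section | Acts at entry? | Names dissociation? |
|---|---|---|---|
| Advance warning: "Study staff and the intervention instructor will make participants aware of the experiences that can occur prior and during their time in the study" | 7 | No screening | No |
| Right to decline an activity | 7 | No | No |
| Instructor-prompted follow-up | 7.2 | No | No |
| Calls in each of two session periods: "Study staff will call participants to inquire about practice and adverse events at least once during this period" | 6.1.3 | No | No |
| PROMIS Anxiety after a positive answer; consult the principal investigators if T rises by more than 9 and exceeds 65 | Appendix A.1 | No | No |
| Weekly check-in until an event resolves | 7.5 | No | No |
| Discontinuation for psychosis or hospitalization for psychological trauma | 8.1 | No | No |
| Stop if 3 or more people have a related serious event | 9.3 | No | No |

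**Exposure.** 32 caregivers + 32 care partners = 64 planned participants, all of whom take the training.

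**Precision cost of an exclusion.** A caregiver cannot start alone: "The primary caregiver will become ineligible for the first intervention session if a care partner does not agree to participate". One exclusion can therefore remove a dyad, 1/32 = 3.1% of the planned number. Section 9.2 uses n = 32 and 85%, and prints a 95% CI of 72.5 to 97.5, a half-width of 12.5 points. The Wald formula is 1.96 × √(0.85 × 0.15 / n):
- n = 32: 1.96 × √(0.1275/32) = 12.37 points (72.6 to 97.4, the plan's interval to within 0.13 point);
- n = 31: 12.57 points;
- n = 30: 12.78 points.

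Each unreplaced dyad costs about 0.2 point of half-width.

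**The case against.** The strongest reply is that the condition fails only if both branches fail, and the second depends on credentials that cannot be seen. A principal investigator, the Study Physician, a committee member or the session listener may be an experienced mental health clinician. The consent form, the screening script and the checklist itself are also unavailable, and any of them might raise the subject. This stands. A reader might infer that the study had no mental health clinician, or that the safety condition was breached in practice. The documents do not support either inference, because the material that would settle it was removed before review. A credential on a roster would still not assign anyone the monitoring duty; that belongs in Section 7, which is visible.

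A second reply is that general safeguards are substantial and Section 7 rates the risks as minimal. The adverse event form asks about any new or worsening emotional problem, so its examples do not rule dissociation out. This stands in part, since such a problem may well be picked up. But these measures react after exposure, and Section 2.2 itself asks for more than instructor support where dissociation is concerned.

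A third reply is that the sentence is rationale, not an eligibility rule. That is correct. It is nevertheless a safeguard that the protocol calls important, and the eligibility section does not carry it forward.

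**Conclusion.** The exclusion branch is not carried out in the visible text: 0 of 11 conditions in 4.1, and no screening step in 6.1.1, address dissociation or mental health for either dyad member. The monitoring branch is undescribed, not shown to be unmet. The existing safeguards are reactive; none screens at entry or names dissociation.

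The gap applies to all 64 planned participants. How many would be susceptible is not stated, so no number at risk is estimated, and no actual harm is shown. The conclusion assumes that 4.1 and 6.1.1 are complete as they appear, with no criterion held only in a document not seen here. A change is warranted because the operative text departs from the protocol's own safety condition and closing the gap is cheap.

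**What to change.** Add one self-report question on dissociation to 4.1 and to the inclusion/exclusion checklist, for caregivers and care partners alike. A positive answer excludes, unless Section 7 assigns a team member who is already a qualified mental health clinician to monitor the program. The session-listening role in 10.2 would be a natural place for that duty. In either case, add dissociation to the possible adverse experiences in Section 7 and to the examples in the emotional-health question of Appendix A.1. If enrolment has closed, record which branch was used and correct the text before the larger interventions this pilot is meant to inform.

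The question fits into the existing caregiver screening call and the care partner screening or consent call. An excluded dyad that is not replaced moves the half-width from 12.4 to 12.6 points, and two such dyads move it to 12.8. Self-report will miss some people. The protocol does not define susceptibility, so treating a positive answer as susceptible is a practical choice that may exclude some who are not. The clinician route costs no dyads, and it needs no new hire only if a qualified person is already on the team, which cannot be seen here.
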